## 10.16 Paired Difference in Pain-Free Subjects

Difference between treatments (LAT8881 – Placebo) for No Headache Pain at each timepoint, Sustained Pain-Free at 24 hours and First Pain-Free Timepoint will be calculated as below for the percentage difference; the numerator represents the difference in the number of subjects.

	Placebo		Total
	Pain free	Pain	
LAT8881			
Pain free	a	b	a + b
Pain	c	d	c + d

Total	a + c	B + d	a + b + c + d
-------	-------	-------	---------------

$$\text{Pain free for placebo (\%)} = \frac{a + c}{a + b + c + d}$$

$$\text{Pain free for LAT8881 (\%)} = \frac{a + b}{a + b + c + d}$$

$$\text{Pain free (LAT8881 - Placebo) (\%)} = \frac{a + b}{a + c + b + d} - \frac{a + c}{a + b + c + d} = \frac{b - c}{a + b + c + d}$$

### 10.17 Preferred Treatment

For subject satisfaction score, the preferred treatment will be flagged based on the treatment period and assigned treatment. I.e., If a subject has chosen 'Treatment period 1' as their preferred treatment, then the corresponding treatment group at period 1 will be flagged as their preferred treatment.

### 10.18 Subgroups for exploratory analysis

Below subgroups will be defined in the analysis datasets and used for the additional exploratory analyses.

- Age at onset: before 15 years and at 15 years or older.

*Age at onset to be calculated as: (Date of episodic migraine diagnosis - Date of birth + 1) / 365.25.*

- Sex group: Male, Female (menstruating), Female (non-menstruating) and Female (postmenopausal)

*For Female subjects, menstruating and non-menstruating will be determined using the start and end dates of the menstrual cycle and the migraine start date. If the migraine start date is between start and end date of menstruation, then the subject will be considered as 'menstruating' and 'non-menstruating' otherwise.*

*Post-menopausal status can be determined by the reasons collected on the diary*

*Any ambiguity in determining the category will be discussed and clarified in the blinded review meeting.*

- Nature of migraine: with aura and without aura.

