Patient satisfaction for each treatment recorded on a 7-point Likert scale and the within-subject difference between treatments will be summarised. The mean difference between treatments will be compared with a paired t-test and the 95% confidence interval for the mean difference will be presented. Additional exploratory analyses to investigate the association between change in headache pain and symptom scores and selected subject baseline characteristics will be undertaken in a similar fashion with descriptive statistics.

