## 4.4 Inclusion/Exclusion Criteria

### 4.4.1 Inclusion Criteria:

*Subjects must meet the following criteria to be entered into the study:*

1. *Males or females aged 18 to 75 years at the time of consent*
2. *Diagnosis of episodic migraine headache at least 12 months ago with or without aura as defined in ICHD-3-beta*
3. *Onset of migraine headache before age 50*
4. *Medical history of 2 - 8 migraine headache attacks per month for the previous 12 months;  $\geq 75\%$  of attacks progress to moderate or severe pain within 2 hours (i.e., rapidly-escalating)*
5. *Minimum 48 hours on average between migraine headache attacks*
6. *Acute headache medication on  $\leq 14$  days/month in the 3 months prior to screening*
7. *Willing and able to comply with all study procedures including completion of a headache diary and a migraine diary on the day of a migraine headache*

8. *Female subjects must be:*
  - a) *of non-child-bearing potential [surgically sterilised or postmenopausal (12 months with no menses without alternative medical cause)] OR*
  - b) *not pregnant, breast feeding or planning to become pregnant AND willing to comply with the medically acceptable contraceptive requirements of the study from Screening to at least 28 days after the last IMP administration*
9. *Male subjects with female partners of childbearing potential must use adequate and highly effective methods of contraception, from screening until 28 days after their last IMP administration.*
10. *Subjects must be sufficiently competent in English to understand the purposes and risks of the study and to provide written informed consent*

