### 7.4 Exploratory Endpoints

- 1. The percentage of subjects who are "sustained pain-free," defined as having no migraine headache pain at 24 hours, with no use of rescue medication and no relapse of headache pain within 24 hours (24-hour sustained pain-free) after administration*
- 2. The time to first pain-free timepoint following treatment with oral LAT8881 compared with placebo to 24 hours post dose, with no use of rescue medication*
- 3. Supplemental analgesic medication use in the 24 hour post treatment period*
- 4. Subject satisfaction with each treatment based on a 7-point Likert Scale, overall preference for Treatment 1 or Treatment 2, and historical comparison with usual treatment*

5. *Association between change in headache pain and symptom scores and selected subject baseline characteristics, including for example, migraine with/without aura, relationship to menstrual cycle*

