##### Difference between treatments:

The difference in absolute scores and change from baseline between both treatments will be summarised by timepoint. Timepoints to be included in this table are: Before IMP was taken (Predose), 30 minutes after IMP taken (t=0.5 hrs), 1 hour after IMP taken (t=1 hr), 1.5 hours after IMP taken (t=1.5 hrs), 2 hours after IMP taken (t=2 hrs), 4 hours after IMP taken (t=4 hrs), 8 hours after IMP taken (t=8 hrs) and 24 hours after IMP taken (t=24 hrs). 95% Confidence interval for the difference between treatments will also be provided.

Difference between treatments will be calculated as mentioned in section 10.15.1.

In DDP: Table 14.2.8.1 to Table 14.2.10.3

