##### Time trend plots:

Time-trend plots will be created for the change from baseline NRS pain and symptom scores over time by treatment and subgroup. Each treatment group within a subgroup will be presented in a separate plot. Both treatments will be displayed side-by-side for comparison. X-axis will be the Timepoint (hours) and Y-axis will be the NRS pain score. Each subject will be presented by a line within the plots

and all subjects within a single group will be presented in the same color. Mean NRS pain score at each timepoint will also be plotted for reference.

Any change in the above analysis will be discussed and finalised in the blinded review meeting.

Subgroups are as defined in section 10.18.

In DDP: Figure 14.2.8

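### Age at onset is derived in years but analysed only as an unexplained split at 15, so its association with response is not estimated and at least about a third of the information is lost if the trend is roughly linear

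*SAP*

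**What the plan says.** Exploratory endpoint 5 (SAP 7.4; Protocol 10.4) is the "Association between change in headache pain and symptom scores" and selected baseline characteristics.

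SAP 10.18 sets the form in which age at onset enters: "Age at onset: before 15 years and at 15 years or older". The value is first derived in years: "Age at onset to be calculated as: (Date of episodic migraine diagnosis - Date of birth + 1) / 365.25". Eligibility gives an upper limit only: "Onset of migraine headache before age 50".

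SAP 11.8.3.4 is the analysis section for this endpoint, and for its factors it says "Subgroups are as defined in section 10.18". It lists descriptive summaries by treatment and subgroup, treatment differences by timepoint and time-trend plots by subgroup. For the differences, "95% Confidence interval for the difference between treatments will also be provided"; I read this as applying within each subgroup. It lists no slope, correlation, interaction term or scatter plot against age at onset. The pain MMRM in SAP 11.8.1.3 has baseline pain score as its only covariate.

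Protocol 14.5 says that the association analyses "will be undertaken in a similar fashion with descriptive statistics". SAP 11.8.3.4 leaves room for revision: "Any change in the above analysis will be discussed and finalised in the blinded review meeting".

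**The concern.** The SAP has a value in years and reduces it to two levels before using it. Onset at 15 and onset at 49 are then treated as the same. No reason is given for the 15-year cut, and one side may hold few subjects in a trial planned for 20 completers.

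The output also does not match the endpoint. A treatment difference with its interval on each side of a cut leaves the reader to compare two intervals by eye. It does not say how the treatment difference changes with age at onset, or how precisely that is known. What is at stake is one exploratory question: whether age at onset influences the response. The primary and secondary results are not affected.

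**Working it through.** **Inputs from the documents.** 20 planned completers, up to 20% non-completion and 26 enrolled (SAP 4.2); two-sided 0.05 for any tests (SAP 8); a cut at 15 years (SAP 10.18). The documents give no power, SD, effect size or distribution of age at onset for this analysis.

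**The plan's own figure.** 20 / (1 − 0.20) = 25, and 26 × 0.8 = 20.8 completers. The stated 26 is consistent with 20 completers, so I use N = 20 pairs.

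**My assumptions.** Age at onset roughly normal; a linear association with the within-subject treatment difference; one outcome per subject; true correlation 0.3 to 0.6.

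**Step 1: information kept by a split.** With share p on the small side, the efficiency relative to the continuous value is φ(z_p)² / [p(1 − p)], where φ is the standard normal density and z_p its p-quantile.

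| Share on small side | Of 20 | Efficiency | Information lost |
|---|---|---|---|
| 50% | 10 | 0.64 (= 2/π) | 36% |
| 30% | 6 | 0.58 | 42% |
| 25% | 5 | 0.54 | 46% |
| 20% | 4 | 0.49 | 51% |
| 15% | 3 | 0.43 | 57% |
| 10% | 2 | 0.34 | 66% |

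The loss is never below 36%. It passes one half at about 20% on the small side.

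**Step 2: could the small side be that small?** If the true share on one side were 10%, 20%, 30% or 40%, the binomial chance that it holds 4 or fewer of 20 is 96%, 63%, 24% or 5%. The documents do not say which share applies.

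**Step 3: the same loss expressed as power.** No test is planned, so this is only a yardstick. Simulation, 40,000 data sets per setting, N = 20:

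| True correlation | Continuous | 2 v 18 | 4 v 16 | 5 v 15 | 10 v 10 |
|---|---|---|---|---|---|
| 0.3 | 25% | 10% | 14% | 15% | 17% |
| 0.4 | 43% | 15% | 21% | 23% | 28% |
| 0.5 | 64% | 21% | 31% | 35% | 42% |
| 0.6 | 84% | 29% | 45% | 51% | 60% |

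The relative loss of power is 28–35% with 10 on the small side, 40–46% with 5, 46–51% with 4 and 59–67% with 2.

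**Step 4: width of the planned subgroup intervals.** The half-width is t(0.975, n − 1) / √n in SDs of the paired difference: 2.48 for n = 3, 1.59 for n = 4 and 0.51 for n = 17. With an assumed SD of 3 NRS points, that is about 7.5 points for n = 3, 4.8 for n = 4 and 1.5 for n = 17. A small side of 3 or 4 would therefore say very little on a 0–10 scale.

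**The case against.** The strongest reply is that nothing planned fails. The protocol calls these analyses descriptive, specifies no formal hypotheses and made no sample size estimation. Power therefore compares a test that I propose with a test that nobody planned. This stands, and it is why the point is one of lost precision.

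Several further points also stand.

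- **Small associations.** At a correlation of 0.2, power is about 13% with the continuous value and 9–10% with 4 to 10 subjects on the small side. Sample size is then the main limit, and neither form is informative.
- **Linearity.** If the truth were a step at the cut, the split would do better. With an assumed step of 1 SD and 20–50% of subjects below it, power is roughly 38–54% for the split and 21–35% for the slope. The protocol's background (section 3.1) describes migraine changing around puberty but does not offer this as the reason for 15. A straight line is not established by the documents either, so both displays are worth having.
- **Scope.** Age at onset is one of three factors in SAP 10.18, and the other two are categorical. Endpoint 5 names aura and menstrual cycle as its examples.
- **Which age.** The SAP formula uses the diagnosis date, and the migraine history items listed in Protocol 9.2 and 11.1.1 include no onset date. As derived, the value is age at diagnosis.

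A reader might infer that the cut loses most of the chance of seeing an association. The documents do not support that. It would need about 4 or fewer of 20 on one side, and they give no distribution. A reader might also infer that the trial cannot answer its question on influencing factors, but that does not follow from a cut on one of three factors.

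Data listings and individual lines in the subgroup plots partly help, but neither shows response against age at onset.

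**Conclusion.** The point holds as a cheap improvement to one exploratory analysis. Age at onset is available in years, is used only as an unexplained two-group split, and is never related to response by any estimate of association. Under a roughly linear trend the split loses at least about a third of the information, and more than half if about 20% or fewer fall on one side. The actual loss is unknown. Keeping the value continuous does not make the question well powered: at 20 pairs, power is 25% to 64% for correlations of 0.3 to 0.5. The figures rest on the assumptions of normality, linearity and correlation size listed in the working, none of which comes from the documents.

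**What to change.** In SAP 11.8.3.4, add a regression of each subject's LAT8881 minus placebo difference in change from baseline NRS pain on age at onset in years. Do this at one or a few timepoints named before unblinding; 2 hours is a natural candidate, as the last scheduled score before rescue medication is permitted. Report the slope with its 95% CI, labelled exploratory, with a scatter plot to check linearity. Keep the 15-year split as a descriptive display and state why 15 was chosen.

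Do not add an age-by-treatment-by-timepoint interaction to the MMRM. It would mean up to seven treatment-slope contrasts from about 20 pairs.

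State in SAP 10.18 that the derived value is age at diagnosis unless an onset date is available, and label the output to match.

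The cost is a few lines of SAP text and one extra output, with no new data collection. The blinded review meeting is already the place for such changes. The downsides are a rough, checkable linearity assumption and that only subjects treated in both periods contribute, as is already true of the treatment differences defined in SAP 10.15.1.

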8.2 Concomitant medications and treatments

8.2.1 Prohibited medications

Medications for migraine prophylaxis are prohibited:

- from 6 months prior to Screening and throughout the study:
 - Calcitonin gene-related peptide pathway monoclonal antibodies CGRP antagonists, eg erenumab (Aimovig)
- from 3 months prior to Screening and throughout the study
 - Antiepileptic drugs including valproate, topiramate
 - Betablockers
 - Triptans (eg naratriptan for premenstrual migraine)
 - Tricyclic antidepressants (TCAs)
 - Botulinum toxin
 - Calcium channel blockers
 - MAO-A inhibitors
 - Nerve blocks
 - Serotonin-norepinephrine (noradrenaline) reuptake inhibitor: eg venlafaxine, duloxetine
 - Selective serotonin reuptake inhibitors, eg fluoxetine, sertraline
- from Screening and throughout the study
 - NSAIDs
- Investigational drugs for prophylaxis or treatment of migraine or other medical conditions

Any other medications which may impact on pain assessments are prohibited if taken within 24 hours prior to taking the dose of IMP.

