9.2 Screening visit (Visit 1)

After written informed consent has been obtained, a unique Screening Number (Subject ID) will be assigned and screening assessments may commence.

During the screening procedure, Days -28 to Day – 1 inclusive, subjects will undergo screening assessments including medical history, height, weight, 12-lead ECG, vital signs, and full physical examination. In addition to eligibility criteria, medical history will include details of history of migraine headaches, average duration (shortest and longest), description of nature (throbbing, aggravating factors, unilateral/bilateral, aura), severity and associated symptoms including most troublesome symptom and relationship to menstrual cycle (menstruating females).

Concomitant medications will be recorded. Blood will be collected for routine haematology and biochemistry screening and, in female subjects of child-bearing potential, to test for pregnancy. A urine sample will be collected for urinalysis.

Subjects deemed likely to be eligible for the trial will be given two diaries after completion of the above screening tests, shown how to record and to list concomitant medications. The headache diary will be used to record menstrual cycles, and onset and nature of headaches (both migraine and non-migraine). In addition, they will be instructed to complete a migraine diary during a migraine headache to collect pain and symptom scores and concomitant medications. Scores will be recorded before taking their usual migraine medication and at 0.5, 1.0, 1.5, 2, 4, 8 and 24 hours after taking their usual migraine medication. The screening diaries will be completed for a minimum of 28 days. If the subject does not experience a migraine headache in this period or menstrual bleeding (menstruating females only), the screening diary period may be extended by 7 days, ie up to 35 days total.

Note that diary entries completed prior to Day 1 will be used only to confirm compliance with diary completion requirements on the day of a migraine headache, to verify the nature of migraine headache and the subject's most troublesome symptom.

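### Relationship to menstrual cycle is collected at screening but enters no planned summary or subgroup, and the attack-timing rule in SAP 10.18 pools premenstrual attacks with unrelated ones

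*SAP*

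**What the plan says.** Exploratory endpoint 5 (Protocol 10.4, SAP 7.4) is the association between change in pain and symptom scores and selected subject baseline characteristics, "including for example, migraine with/without aura, relationship to menstrual cycle". Protocol 9.2 has the screening migraine history record "severity and associated symptoms including most troublesome symptom and relationship to menstrual cycle (menstruating females").

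The SAP does not carry that item forward. SAP 11.4 names the migraine-history variables to be summarised, and this one is not among them. SAP 10.18 defines the subgroups for the association analysis as age at onset, aura, and "Sex group: Male, Female (menstruating), Female (non-menstruating) and Female (postmenopausal"). The two middle categories come from diary dates: "If the migraine start date is between start and end date of menstruation", the subject counts as menstruating, and in every other case as non-menstruating. The section adds "Any ambiguity in determining the category will be discussed and clarified in the blinded review meeting".

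SAP 11.8.3.4 then summarises scores by subgroup within treatment, gives LAT8881-minus-placebo differences with 95% confidence intervals, and lets changes to this analysis be settled at the blinded review meeting.

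Premenstrual migraine appears in Protocol 8.2.1 as an example among the prohibited prophylactics: "Triptans (eg naratriptan for premenstrual migraine").

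**The concern.** The endpoint asks about a characteristic of the subject, known before randomisation. The subgroup describes the timing of one treated attack, observed after randomisation. These are different variables. A woman whose migraines usually follow her cycle can treat an attack at mid-cycle, and a woman with no such pattern can treat one on a bleeding day.

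The attack-timing rule is also narrow. An attack that starts the day before bleeding is non-menstruating without any doubt, so the provision for ambiguous cases does not reach it. Attacks plausibly tied to the cycle then sit on both sides of the two female categories that a reader will compare.

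At stake is whether the exploratory table can say anything about the relationship the endpoint names. Nothing in the primary or secondary analysis is affected.

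**Working it through.** **What the documents settle.** Three places, set side by side:

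- Collected: relationship to menstrual cycle, in the screening migraine history (Protocol 9.2).
- Named for analysis: the same relationship, as an example baseline characteristic (SAP 7.4).
- Analysed: start of the treated attack on a bleeding day (SAP 10.18). The screening item is absent from SAP 10.18 and from the SAP 11.4 summary.

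This mismatch needs no arithmetic.

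**The plan's own figure.** None is given for the subgroup. The only size stated is 20 completers from 26 enrolled: 20/(1 − 0.20) = 25, and 26 corresponds to 1 − 20/26 = 23% loss, so the stated figure is reproduced to within one subject.

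**Size of the pooling.** All inputs here are assumptions, not figures from the documents: a 28-day cycle, b = 4 to 7 bleeding days, a premenstrual window of w = 2 to 3 days, and a daily attack risk in both windows r = 1 to 3 times that on other days. The share of non-menstruating attacks that are premenstrual is

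f = w·r / (w·r + 28 − b − w)

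| b | w | r = 1 | r = 2 | r = 3 |
|---|---|---|---|---|
| 4 | 2 | 2/24 = 8% | 4/26 = 15% | 6/28 = 21% |
| 4 | 3 | 3/24 = 12.5% | 6/27 = 22% | 9/30 = 30% |
| 5 | 2 | 2/23 = 9% | 4/25 = 16% | 6/27 = 22% |
| 5 | 3 | 3/23 = 13% | 6/26 = 23% | 9/29 = 31% |
| 7 | 2 | 2/21 = 10% | 4/23 = 17% | 6/25 = 24% |
| 7 | 3 | 3/21 = 14% | 6/24 = 25% | 9/27 = 33% |

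**From share to dilution.** Let bleeding-day attacks differ from unrelated attacks by Δ, and premenstrual attacks by s·Δ. The non-menstruating mean shifts by f·s·Δ, so the difference seen is Δ(1 − s·f). With f = 16% (b = 5, w = 2, r = 2):

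- s = 1 (like bleeding-day attacks): 84% of Δ remains.
- s = 0.5: 92% remains.
- s = 0 (like other attacks): 100% remains, no dilution.
- s = −0.5: 108%, an exaggeration.

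The 8% to 33% range therefore applies only at s = 1.

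**Against sampling error.** Assume 15 menstruating women with one attack each per period, and an SD of change of 2 to 3 NRS points. With b = 5, w = 2, r = 2, the bleeding-day group has 15 × 10/35 = 4.3 attacks and the other 10.7. The standard error is SD × √(1/4.3 + 1/10.7) = SD × 0.57, or 1.1 to 1.7 points. A true difference of 1 to 2 points loses 0.16 to 0.32 points. In the corner of the grid with most dilution (b = 7, w = 3, r = 3), 2 points lose 2 × 9/27 = 0.67. The groups there are 15 × 21/48 = 6.6 and 8.4, and the standard error is SD × 0.52, or 1.0 to 1.6 points. The loss stays below one standard error throughout.

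**The case against.** The strongest case against has five parts.

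- **The item is not ignored.** A reader might infer that it is never used. The documents do not support that: migraine history is listed by subject (SAP 11.4), as are all eCRF data (SAP 8). It is absent from summaries and subgroups only.
- **No contrast is planned.** A reader might infer that the plan dilutes an association against a reference group. The SAP names no reference group and plans no between-subgroup difference, interaction or test. Any blurring is of summaries read side by side, and only if premenstrual attacks respond like bleeding-day attacks. The documents are silent on that, and the prohibited-drug example gives no window and no effect.
- **The endpoint leaves a choice.** It speaks of selected characteristics and gives examples. Prospective diary dates are a defensible source beside recalled history. This stands, but it supports keeping the diary rule as well, not leaving out the baseline item that the endpoint names.
- **The blinded review meeting can change the analysis.** True under SAP 11.8.3.4. That clause permits the change; it does not make it.
- **The dates may be incomplete.** A premenstrual attack is known only from bleeding that starts afterwards. Period 2 diaries come back at Visit 4, within 5 business days of dosing, and the Visit 5 call covers only adverse events and medications. A later onset may go unrecorded. This stands and calls for an unknown category.

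The restriction in Protocol 9.2 on screening data does not block the fix: it covers diary entries before Day 1, not the history item.

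**Conclusion.** The point holds, and it is minor. A baseline item that the endpoint names and the trial collects enters no planned summary or subgroup, and the rule used in its place pools attacks just before bleeding with attacks unrelated to the cycle. That much follows from the documents alone.

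The size does not. The 8% to 33% blurring rests on assumed cycle, bleeding, window and risk values, and on premenstrual attacks responding exactly like bleeding-day attacks. It is zero if they respond like other attacks. In either case it is less than the sampling error to be expected with about 20 completers, in an analysis that is descriptive. The stronger statement, that the association is diluted, is therefore not established. Not knowing how these attacks respond is a reason to show them separately.

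**What to change.** Before unblinding:

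1. Add relationship to menstrual cycle (menstruating females) to the SAP 11.4 summary, and make it a subject-level baseline subgroup in SAP 10.18, with categories as recorded in the eCRF.
2. Keep the bleeding-day rule in SAP 10.18 as a descriptor of the attack. Derive the days from attack start to the nearest recorded bleeding onset, and show premenstrual attacks as a separate row, with the window fixed by the sponsor. Use an unknown category where the next onset may fall after the diary is returned, that is, where the diary comes back before the window has run out and no onset is recorded.

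Both changes can be settled at the blinded review meeting that SAP 11.8.3.4 provides for. They need SAP wording and one derived variable, and no new data collection.

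The cost is one or two more rows in a sparse table. With the 15 women assumed above and b = 5, w = 2, r = 2, the premenstrual row would hold about 15 × 4/35 = 1.7 attacks per period, so it should be read as description only.
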